All subjects will be analyzed according to the intention-to-treat [ITT] principle. A participant will be considered evaluable and will be included in the intention-to-treat analysis if the participant has documented at least 8 sessions of their designated TENS treatment (about 4 times a week of TENS therapy). Analyses that take into account the actual treatment received (e.g., non-compliance, etc.) will be carried out as a secondary analysis (per protocol [PP] analysis).

Primary Statistical Objective:

The primary objective of the study is to compare the three TENS treatment groups after two weeks of active treatment, with respect to:

The change in VAS and GUPI pain questionnaires from baseline to after two weeks of

therapy.

The proportion of responders after two weeks of therapy.

Secondary Statistical Objectives:

Secondary objectives include comparison of the three treatment groups with respect to the rating of VAS and GUPI scores, separately, over time (by weekly diary entries). Analysis will be carried out to determine if there are time-dependent changes in questionnaire scores across the three TENS treatment groups. Urinary symptoms and individual pain site questions will be noted.

Pairwise comparisons of TENS groups will also be carried out to compare each arm with one another using Tukey's multiple comparison tests.

We will again collect data at 1,2-, and 3-months post-trial, asking how much the TENS has been used, to assess durability.

Outcome Variables and Schedule of Assessments:

The primary outcome variable of interest is participant's percentage change in VAS and GUPI from before treatment to the end of 2 weeks of active TENS. Also evaluated will be the response to treatment each week during the 14-day TENS therapy period and the 2 weeks of observation. A participant is said to have a favorable response to the treatment if he/she has a decrease of at least 2 points on the VAS or 1 point on the GUPI question #9 from baseline to after two weeks of TENS therapy. Change in outside interventions will not be permitted during the study but stable therapies will be maintained (e.g., medications).

Demographics and participant characteristics will be collected at baseline (age, gender, medical history, surgical history, current medications, site of pain, duration of chronic pelvic pain). The following outcomes will be measured at baseline, at each week, and at 3 months after the TENS therapy month:

- VAS Weekly Scores
- GUPI Weekly Scores

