Statistical Methods

For the primary objectives:

- Analysis of variance with a fixed effect of treatment with Tukey's multiple comparison test will be used to test for differences in the reduction in genitourinary symptoms among the three treatment arms. Reduction will be parameterized as a relative change from baseline to after the two weeks of treatment. VAS pain response before and after treatment will be compared among the three groups using repeated measures ANOVA with Tukey's multiple comparison tests.
- The Chi-square test or Fisher's exact test, as appropriate, will be used to compare the rates of response among the three treatment arms at the end of the 14-day treatment period.

For the secondary objectives, a repeated measures analysis of variance will be used to analyze the outcomes of interest on a week-to-week basis (improvement in GUPI scores). A treatment-by-time interaction will be examined to determine if the patterns of change in GUPI and VAS scores over time differ across groups. Adjusted pairwise comparisons (Tukey or Bonferroni method) will be used to compare treatment groups to one another.

Data transformations may be applied, if necessary, in order to meet the required standard model assumptions.

Sample Size Considerations

Power: The number of participants needed was based on a power calculation (ANOVA with 2-tailed alpha of 0.05) assuming that the minimally important difference to detect among the three groups in the change in VAS score would be at least one within-group standard deviation of the change in score at 14 days. With 21 participants per group the power is estimated at 81%. We propose to randomize 25 per group assuming the dropout rate may be as high as 20%.

Based on investigator expertise and some published studies, we assume that the proportions of responders based on our criteria of a “favorable response” for each of the three TENS groups will be around 40 % (1,2,4,7,10). In our study we are aiming for at least a 40% response rate in our complex and refractory population.

Conduct of the study

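### Two or three primary outcomes share a single stated alpha of 0.05 with no rule across them, and the primary VAS and GUPI scores and change metric are not fixed

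*Combined protocol and SAP*

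**What the plan says.** **Which outcomes are primary.** Under Primary Statistical Objective (section D), the plan says "The primary objective of the study is to compare the three TENS treatment groups after two weeks of active treatment" with respect to change in VAS and GUPI and, as a further item, "The proportion of responders after two weeks of therapy". Under Statistical Methods, the part for the primary objectives gives an ANOVA for genitourinary symptoms, a repeated measures ANOVA for VAS, and a chi-square or Fisher test that "will be used to compare the rates of response among the three treatment arms at the end of the 14-day treatment period". Under Outcome Variables and Schedule of Assessments, however, the primary outcome variable is only the "percentage change in VAS and GUPI from before treatment to the end of 2 weeks of active TENS". Response follows separately: "Also evaluated will be the response to treatment each week during the 14-day TENS therapy period and the 2 weeks of observation".

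**Error control.** Sample Size Considerations gives a two-tailed alpha of 0.05 for one ANOVA. Tukey's test (Tukey or Bonferroni for the secondary analyses) is planned for comparisons between arms. Nothing addresses several outcomes jointly.

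**Metric.** Outcome Variables uses percentage change for both scores. Statistical Methods says of genitourinary symptoms: "Reduction will be parameterized as a relative change from baseline to after the two weeks of treatment". For VAS it says: "VAS pain response before and after treatment will be compared among the three groups using repeated measures ANOVA". The power calculation uses change in VAS score, in within-group SD units.

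**Scores and baseline.** The appendix form has four VAS items, each 0-10: last 7 days, right now, best this week and worst day this week. GUPI yields pain, urinary and quality-of-life subscales and a total. The Specific Aim (section A) names all three subscales, the primary objective refers to GUPI as a pain questionnaire, and the methods refer to genitourinary symptoms. The secondary objectives add: "Urinary symptoms and individual pain site questions will be noted". Section B combines Weeks 1 and 2 into a 14-day control period without saying how the two weekly values become one baseline.

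**The concern.** The trial asks which of three frequencies works best. If VAS separates the arms and GUPI or response does not, or the reverse, the plan has no rule for which result answers the question. Any one of them could be reported as meeting the primary objective, and the error rate of that approach exceeds the nominal 5%.

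The open definitions add to this. With four VAS items, several GUPI scores, an unstated baseline formula and more than one change metric, the primary result depends on choices that could be made after the data are seen. The 81% power refers to change in VAS score. It does not carry over automatically to percentage change, to GUPI or to response.

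**Working it through.** **1. Reproduce the stated power.** Inputs from Sample Size Considerations: three arms, 21 per arm, alpha 0.05, a difference of 1 SD among the groups. The pattern of the three means is not given. For a one-way ANOVA the noncentrality is n × Σ(mean − grand mean)², in SD units, with 2 and 3(n − 1) degrees of freedom.

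- Means 0, 0.5, 1 SD: 21 × (0.25 + 0 + 0.25) = 10.5, with 2 and 60 df. Power is 81.5%, which matches the stated 81%.
- Means 0, 0, 1 SD: power is 91.5%, which does not match.

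The first pattern is therefore taken as the one behind the plan.

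**2. False-positive rate across outcomes.** For independent tests at 0.05:

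- two tests: 1 − 0.95² = 0.0975;
- three tests: 1 − 0.95³ = 0.1426.

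The outcomes are correlated, so the actual rate is lower. It was simulated with no true difference, 21 per arm and 100,000 trials per setting. VAS change, GUPI change and change in GUPI question 9 were normal with a common correlation. A responder was anyone beyond a cut-off on VAS or question 9, set to give 40% overall (the response rate that the plan assumes). The correlations are assumptions. The value 0.9 is included because GUPI item 4 (average pain over the last week, 0-10) is close to the last-7-days VAS item.

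| Assumed correlation | VAS or GUPI | VAS, GUPI or response | Any Tukey pair on VAS or GUPI |
|---|---|---|---|
| 0.3 | 9.5% | 13.5% | 9.6% |
| 0.5 | 9.1% | 12.7% | 9.1% |
| 0.7 | 8.5% | 11.6% | 8.5% |
| 0.8 | 7.8% | 10.8% | 7.8% |
| 0.9 | 7.1% | 9.9% | 7.2% |

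The last column shows that Tukey's method leaves the excess in place, because it works within one outcome. Repeat simulations agreed to within about half a percentage point.

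**3. A different error: wrongly naming 100 Hz best.** Suppose the event is 100 Hz being Tukey-superior to both other arms on VAS or GUPI. The false-positive rate is then 0.2-0.3% with all arms equal. It is 1.4-1.9% if 50 and 100 Hz are equal and both beat 20 Hz by 1 SD (correlations 0.3 to 0.9, response not included).

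**4. Zero baseline.** Section B admits a participant with 4 or more on any VAS item, or 3 or more on GUPI question 9. Someone can therefore enter with 0 on a particular VAS item, such as best this week. Percentage change in that item is then undefined.

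**5. Power if VAS and GUPI both stay primary at 0.025 each.** Means 0, 0.5, 1 SD:

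- 21 per arm: 72.6%;
- 25 per arm: 81.5%, the smallest number reaching 80%;
- with 20% dropout, 25 / 0.8 = 31.25, so 32 randomized per arm (96 in total, against 75 planned).

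With means 0, 0, 1 SD, power at 21 per arm is 85.8%, and 19 evaluable per arm reach 80%.

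**The case against.** The strongest reply is that the 10-14% range rests on the least favorable reading. The outcome definition names only VAS and GUPI and lists response as also evaluated, and the sample size text treats 40% response as a benchmark expected in every arm, not as a powered difference. That stands: the documents support two primaries at least as well as three, and the firmer range is 7-10%.

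Second, no text says that any one significant test means success. That also stands, so the rates are conditional. But no text states a different rule, and that absence is the problem.

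Third, a reader might infer a 10-14% chance of wrongly declaring 100 Hz best. The documents and the figures do not support that. The stated hypothesis is that 100 Hz beats both other arms, and the false-positive rate for that event is far lower (step 3). The plan does not make that event its decision rule either.

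Fourth, baseline is not wholly open. Section B says that Weeks 1 and 2 are combined, and only the formula is missing. Similarly, the zero-baseline problem for VAS arises only under the percentage-change label in Outcome Variables, since Statistical Methods compares VAS before and after. A GUPI total at screening is at least 3 for anyone who qualifies on question 9. The open GUPI score and baseline formula would, alone, be no more than missing detail.

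Finally, one may argue that VAS is implicitly primary because it was powered. No section says so.

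**Conclusion.** The concern holds. Two or three outcomes carry primary status depending on which paragraph is read, each has its own test, and nothing governs them jointly. If any significant overall test counts, the false-positive rate is about 7-10% for two outcomes and about 10-14% for three, against 5%. Those ranges rest on assumed correlations of 0.9 to 0.3 and 21 evaluable per arm. The excess over 5% is present throughout the range.

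Separately, the primary metric is stated in conflicting ways, no VAS item is named, the GUPI score is described differently in three places, and the baseline formula is absent. These gaps need no assumption to establish. The point should be fixed before data are seen. It does not call the trial's design or number randomized into question.

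**What to change.** **Preferred.** Name one primary outcome: score change on one named VAS item (for example the last-7-days item) from the mean of Weeks 1 and 2 to Week 4. Test it with one ANOVA of change by group at 0.05, followed by Tukey comparisons of the arms. With one baseline and one end value, this is the same as the group-by-time test in the planned repeated measures ANOVA, and it matches the power basis. Score change also removes the zero-baseline problem. Make one named GUPI score the first secondary outcome, tested at 0.05 only if the primary is significant. Report response and the remaining VAS and GUPI scores as secondary with 95% confidence intervals. Use the same terms in the Specific Aim, Primary Statistical Objective, Outcome Variables and Statistical Methods.

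The cost is wording only, with no change to the 25 per arm. The downside is that GUPI and response can no longer carry a primary claim alone.

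**Alternative.** If VAS and GUPI both stay primary, test each at 0.025, make response secondary, fix the same definitions, and restate power as 72.6% at 21 evaluable per arm with means 0, 0.5 and 1 SD. Because 80% would take 32 randomized per arm at 20% dropout, the change here is to restate the power, not to enrol more.

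Under either option, 20% dropout from 25 leaves 25 × 0.8 = 20 per arm, not 21 (79.3% for one primary at 0.05, means 0, 0.5 and 1 SD). That is a separate point, which this change does not address.

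### The primary VAS outcome is defined as percentage change, but the named VAS test amounts to a test of point change, and no rule covers a zero baseline

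*Combined protocol and SAP*

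**What the plan says.** All of this is in the combined protocol and SAP.

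- **Primary Statistical Objective (section D):** the arms are compared on "The change in VAS and GUPI pain questionnaires from baseline to after two weeks of" therapy. The scale of change is not given.
- **Outcome Variables and Schedule of Assessments (section D):** the primary variable is "percentage change in VAS and GUPI from before treatment to the end of 2 weeks of active TENS". The response rule in the same section is in points: a fall of 2 on VAS or 1 on GUPI question 9.
- **Statistical Methods (section D), primary objectives:** an ANOVA is used to "test for differences in the reduction in genitourinary symptoms among the three treatment arms", and "Reduction will be parameterized as a relative change from baseline to after the two weeks of treatment". The next sentence treats VAS separately: "VAS pain response before and after treatment will be compared among the three groups using repeated measures ANOVA". A later sentence adds: "Data transformations may be applied, if necessary, in order to meet the required standard model assumptions".
- **Sample Size Considerations (section D):** the effect is the "minimally important difference to detect among the three groups in the change in VAS score", set at "at least one within-group standard deviation of the change in score at 14 days". Power is given as 81% with 21 per group.
- **Screening Day 7/Week 1 (section B):** a participant qualifies with 4 or more on any one VAS score, or with 3 or more on GUPI question 9. Weeks 1 and 2 together form the control period.
- **Appendix (section J):** the VAS form has four items scored 0 to 10 (last 7 days, right now, best this week, worst day this week), each with 0 meaning no pain.

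The plan does not say which VAS item is analysed or how the two baseline weeks are combined.

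**The concern.** The trial exists to decide which of three frequencies works best. If the outcome section and the methods section point to different VAS scales, the same data give two primary VAS results. They can differ on significance and on which arm comes first, and the choice between them would be made after the data are seen.

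Percentage change also divides by the baseline score. It is unstable when that score is low and cannot be computed when it is zero. An entry rule that is met by any one of several scores does not keep the analysed score away from zero.

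**Working it through.** **1. The plan's own power figure.** Inputs from Sample Size Considerations: three groups, 21 per group, alpha 0.05, largest difference 1 SD of change. Assumption: the middle arm lies midway, so the means are 0, 0.5 and 1 SD. Noncentrality = 21 × (0.5² + 0² + 0.5²) = 10.5, with 2 and 60 degrees of freedom. The noncentral F distribution gives 81.5%, which agrees with the stated 81%. The effect is in SD units of the change in VAS score, so the figure is not wrong; the plan just does not say whether that change is in points or percent.

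**2. What the VAS test tests.** Take one before and one after score per participant. The group-by-time term of a repeated measures ANOVA compares the arms on after minus before. On generated data with 21 per arm, its F was 0.29568, and the F of a one-way ANOVA on point change was also 0.29568. The named test is therefore a point-change test. Nothing in it divides by baseline.

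**3. Whether the scale can change the ranking.** Percentage change = (after - before) / before.

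| Pair of participants | Percentage change | Mean percentage | Mean points |
|---|---|---|---|
| 4 to 2, 5 to 3 | -50%, -40% | -45% | -2.0 |
| 10 to 6, 9 to 6 | -40%, -33.3% | -37% | -3.5 |

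Percentage change favours the first pair and point change the second. In the same way, the 2-point response is -50% from a baseline of 4 but -20% from a baseline of 10.

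**4. Whether a zero baseline can occur.**
- Entry on the worst-day item at 4 or more leaves the best-this-week and right-now items free to be 0.
- Entry on GUPI question 9 alone leaves all four VAS items free to be 0.
- The sentence on transformations concerns model assumptions and does not say what to do when the denominator is zero.
- The documents give no rate. If the rate per participant were 0.5%, 1%, 2% or 5% (assumed), the chance of at least one zero among 75 is 1 - (1 - rate)^75 = 31%, 53%, 78% or 98%.
- The GUPI total is at least 3 after entry on question 9, so the problem does not arise there by that route.

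**5. Power under the preferred fix.** Let baseline be the mean of Weeks 1 and 2. Assume equal SDs (set to 1) and equal correlation r between any two weeks.
- Variance of change = 1 + (1 + r)/2 - 2r = 1.5(1 - r).
- ANCOVA residual variance = 1 - 2r²/(1 + r) = (1 - r)(1 + 2r)/(1 + r).
- Ratio of the second to the first = (1 + 2r) / [1.5(1 + r)].
- Noncentrality = 10.5 / ratio, with 2 and 58 degrees of freedom (baseline and gender use 2).

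| r | Ratio | ANCOVA power, 21 per group |
|---|---|---|
| 0.5 | 0.889 | 86% |
| 0.7 | 0.941 | 84% |
| 0.9 | 0.982 | 82% |

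Unadjusted power for the same 1-SD spread in change is 81.5%.

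**The case against.** **The relative-change sentence may be meant for VAS too.** It follows the genitourinary ANOVA and comes before the VAS sentence, which names before and after scores and a different model. The natural reading keeps it with genitourinary symptoms. On the other reading, the zero-baseline gap would still be open.

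**The equivalence in step 2 is conditional.** This stands. It holds for the group-by-time term with one before and one after score. The primary bullet names no interaction term (treatment-by-time appears only under the secondary objectives), and two baseline and two treatment weeks are collected. But no version of a repeated measures ANOVA on VAS scores is an analysis of percentage change.

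**Zero baselines may be rare.** This largely stands. A reader might infer that many participants would be lost; the documents do not support that. For the last-7-days item averaged over two weeks, simulations under assumed inputs put the rate at 0 to 1.4%. It is likelier for the best-this-week or right-now items. If the four items were summed, anyone entering on a VAS item could not have a zero Week 1 composite. The gap is subsidiary to the scale conflict.

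**Any two correlated tests sometimes disagree.** This also stands. In an additive simulation under assumed inputs (20 per arm, mean pain 4 to 6, SD 2 to 2.5, correlation 0.5 to 0.7), point and percentage change disagreed on p < 0.05 in 7 to 13% of trials. Point change and ANCOVA disagreed in 3 to 7%. Not all of the disagreement is due to the percentage scale, so the case rests on the undefined outcome and not on a simulated rate.

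**ANCOVA goes beyond what the defect requires.** It does. It is a preference, and a smaller repair is enough.

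**Conclusion.** The conflict is real and confined to VAS. The outcome section declares percentage change, and the methods section tests VAS on before and after scores. Simple arithmetic on permitted scores shows that the two scales can order groups differently. How often this would happen in the trial cannot be known from the documents, which give no VAS baseline mean or SD. The missing zero-baseline rule is a secondary gap of unknown but probably small size, depending on the item chosen. This should be fixed, but it does not threaten feasibility.

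Three stronger readings are not supported:
- **That GUPI has the same conflict.** The outcome and methods sections agree on relative change for genitourinary symptoms.
- **That the power calculation is wrong.** It reproduces at 81.5% for a 1-SD spread; only its scale is unstated.
- **That ANCOVA would bring a large gain in power.** The ratio (1 + r)/2 gives 91%, 88% and 84% at r = 0.5, 0.7 and 0.9, but it applies to a single-week baseline. With the two-week mean the gain over 81.5% is about 0.6 to 4.5 points.

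**What to change.** Use one VAS scale in the outcome, methods and sample size sections.

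**Preferred:**
- Make the primary VAS comparison the Week 4 score by ANCOVA, with treatment, baseline VAS and gender (the stratification factor), and Tukey comparisons on the adjusted means.
- Name one VAS item, for example the last-7-days item, which covers the whole week.
- Define baseline as the mean of Weeks 1 and 2 on that item.
- Use the same item and baseline in the 2-point response rule.
- State that the 81% refers to a 1-SD spread in unadjusted VAS point change.
- Report percentage change descriptively in participants with a non-zero baseline, with the number left out.

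**Minimum, if percentage change stays primary:** test VAS on percentage change in Statistical Methods as well, and state a zero-baseline rule. The item and baseline still need naming.

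Analysing GUPI by ANCOVA is optional.

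**Cost:** wording only. Both baseline weeks, Week 4 and gender are already collected, and the sample size does not change. Under the preferred fix, results are in points instead of percent, and power may be a few points below that of percentage change if both effect and variation are proportional to baseline.

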The participants will be randomized into three groups of 25 participants each. The randomization will occur in blocks so that if we need to terminate the study early there will be an equal number of participants in each group. The size of the blocks will also be kept secret for allocation concealment purposes. The randomization will be stratified by gender so that there is an equal number of participants from each gender in each group, reducing potential for gender as a confounding variable. Group 1 will be the low frequency set at 20 Hz. Group 2 will be the medium frequency set at 50 Hz. Group 3 will be the high frequency set 100 Hz. There is no sham group in this study as it has previously been found that posterior tibial TENS is effective and lasting. As such, all participants will be treated as a matter of routine medical care for pelvic pain. We will use a fixed pulse width of 200 microseconds (uS), with continuous rather than biphasic stimulation based on input from 5 colleagues with expertise in neurophysiology and TENS and on the above literature review. We will aim to recruit 25 participants per group for a total of 75 participants.

Study Procedures

Participants with chronic/persistent pain that has been continuous or recurrent for at least three months (in accordance with EAU Guideline definition) who have failed first line treatment will be advised of the study. All participants will be asked if they have an adhesive allergy and medical record reviewed for this allergy as this will exclude them from the study. A detailed explanation of the purpose of the study, along with the risks and benefits of TENS will be given to the participant by a provider prior to obtaining informed consent for enrollment into the study. After informed consent has been obtained, if the participant is of childbearing potential, a urine pregnancy test will be conducted. The participant will be excluded from participation if pregnant and referred for appropriate care.

Study Schedule Overview:

	Standard Visit Billed in Part to Insurance	Just a Study Visit	Virtual Phone or Video is an Option	In Person Only	Questionnaires: 1-10 pain scores and GUPI	Usage Chart Completed (During phase when TENS being Used)	Treatment Map Completed / Updated with Dates	Adjusting TENS Settings Permitted	New Treatments outside of pre-existing treatment and TENS Permitted
Week 1 – Phone Call in Response to Mailer		√	√		√		√		
Week 1 – Occurring as Part of Regular Office Visit	√		√		√		√		

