Week 2	√			√	√				
Week 3		√	√		√	√	√		
Week 4	√		√		√	√	√		
Optional Week 8		√	√		√	√	√	√	√
Optional Week 12		√	√		√	√	√	√	√
Optional Week 16	√		√		√	√	√	√	√

Screening Day 7/ Week 1 (in clinic or virtual): The first data points (Day 0) will take place in the clinic during the participant’s routine visit or at the time of the participant’s phone call seeking participation. If during a phone call seeking participation, this will be considered a study phone call, not a billable visit. The participant will fill out the VAS and GUPI. The participants will be taught how to fill out the pain assessment questionnaires (the VAS and GUPI, validated tools for measuring genitourinary pain and symptoms respectively). This can be done via paper to be brought into the office at their next checkup or via an emailed link through Qualtrics and uploaded to a spreadsheet in a protected AMC OneDrive. The baseline pain logs will be reviewed for sufficient severity of pain episodes and the participant will be randomized into the study if their pain is above the designated threshold: participants who record a pain scale of 4 or higher on any of the VAS scores or QOL score of 3 or higher on the GUPI question #9 will be eligible for the TENS study. Those who record lower scores will be ineligible for the TENS study but will be offered therapy in according to the AUA/EUA guidelines using the recommended second or third line therapies for their specific pain etiology, including a trial of a TENS unit.

The GUPI and VAS will be collected at this time; this will record the participant’s pain 1 week prior to the study and will be considered Day 7/week 1. The week 1 of screening will be combined with the first week of baseline measurement (week 2) for a 2-week lead-in.

Participants will be taught how to complete a usage log (stating if the TENS was used each day and for how long in minutes) and will be asked to repeat this weekly. Participants will complete

an inventory (the Treatment Map) of treatments tried prior to the TENS, throughout the study, and at the end.

Baseline Day 14/ Week 2: If the participant enrolls, they will be asked to continue logging pain (VAS and GUPI, on paper or via Qualtrics) for one week, with the week 1 screening and the week 2 baseline week totalling a 14-day control period. The control period will represent data (2 weeks of VAS and GUPI) with only baseline treatments and no TENS unit.

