The objective of this study is to evaluate which pulse rate (frequency) is the most efficacious in transcutaneous electric nerve stimulation (TENS) as a therapeutic option for pelvic pain. The

proposed study will be a randomized clinical trial. There will be three treatment arms with no sham or control:

- 1. Group1: TENS frequency is set to 20 Hz
- 2. Group2: TENS frequency is set to 50 Hz
- 3. Group3: TENS frequency is set to 100 Hz

The study will be conducted for a total of 4 weeks (28 days, including the data for the week prior to the initial consent, week 1), followed by a 90-day observational period.

1. Baseline Measurement of chronic pain using the VAS and GUPI with baseline treatment for 7 days [Week 1 (at first visit, data from week prior) then at Week 2 as a control period]

2. Active measurement of chronic pain using the VAS and GUPI as well as weekly usage logs during TENS treatment for 2 weeks [Week 3-4]

3. Durability: We will again collect data at 1, 2, and 3 months after the week visit for those who elect to continue, repeating the VAS and GUPI and treatment inventory, asking how much the TENS has been used and at what setting, to assess durability and observe participant-directed settings.

RANDOMIZATION

Subjects will be randomly assigned with equal probability to one of the three study groups. Randomization will utilize a web site (www.randomization.com) to provide randomization. Randomization will occur in blocks so that if the study needs to be terminated early there is an equal number of participants in each group at the time of termination. Also, we will stratify groups by gender so that there is an equal number of participants from each gender in each group to help limit this confounding variable. Allocation-concealment will be achieved by using sealed envelopes opened only after subjects are enrolled. Record keeping will be from participant responses via Qualtrics before and during TENS treatment. The scoring of the VAS and GPI scales, the compliance rate (used TENS or not), and any participant comments are recorded. Participant demographic will include age, gender, and pertinent urological history, if any.

BLINDING

There will be single blinding. Study participants/caretakers will not know which frequency has been assigned.

INTENTION-TO-TREAT

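### The plan stratifies by gender and records two pre-TENS weeks, but no test uses gender or a baseline covariate, so the VAS comparison may lose some precision

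*Combined protocol and SAP*

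**What the plan says.** Section B (Study Design) states: "The randomization will be stratified by gender so that there is an equal number of participants from each gender in each group", with the aim of "reducing potential for gender as a confounding variable". The Randomization part of section D repeats the aim: "an equal number of participants from each gender in each group to help limit this confounding variable".

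Study Procedures provides two sets of pre-treatment scores: "The week 1 of screening will be combined with the first week of baseline measurement (week 2) for a 2-week lead-in".

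Outcome Variables defines the primary outcome as the "percentage change in VAS and GUPI from before treatment to the end of 2 weeks of active TENS". Statistical Methods then lists the tests:

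- **GUPI:** "Analysis of variance with a fixed effect of treatment", applied to a relative change ("Reduction will be parameterized as a relative change from baseline to after the two weeks of treatment").
- **VAS:** a repeated measures ANOVA of the scores before and after treatment.
- **Responders:** a chi-square or Fisher test across the three arms.
- **Secondary:** a week-by-week repeated measures ANOVA with a treatment-by-time interaction.

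None of these names gender, or baseline as a covariate. Where the section speaks of adjusted comparisons, it means Tukey or Bonferroni control of multiplicity.

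**The concern.** A factor worth balancing at randomisation is normally carried into the analysis. If it is prognostic and left out, its variance stays in the error term although the arms have been balanced on it, and the test becomes conservative. Likewise, a baseline used only to form a difference or a ratio usually removes less noise than the same baseline used as a covariate.

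What is at stake is power in a small trial. Sample Size Considerations gives 81% at 21 per arm. Randomising 25 and losing the plan's own 20% leaves 25 × 0.8 = 20. The data for adjustment are already being collected.

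**Working it through.** **Inputs from the plan.** Three equal arms, alpha 0.05, a difference of 1 within-group SD of the change in VAS, 21 per arm, 25 randomised, up to 20% dropout.

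**Assumed, because the documents do not give them.** The correlation r between weekly scores (taken as equal for all pairs of weeks), the ratio k of the weekly baseline SD to the Week 4 SD, the share of variance explained by gender, and a middle arm lying midway.

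**1. The plan's figure.** Arm means are −0.5, 0 and +0.5 SD, so the noncentrality is λ = n × (0.25 + 0 + 0.25) = 0.5n.

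- n = 21: λ = 10.5, df 2 and 60, power 81.5%. The stated 81% reproduces.
- n = 20: λ = 10.0, df 2 and 57, power 79.3%.
- n = 20, two error df spent on covariates that explain nothing: df 2 and 55, power 79.2%. The cost is 0.1 point.

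**2. VAS with baseline as covariate.** With Week 4 variance set to 1, the mean of two baseline weeks has variance vb = k²(1 + r)/2 and covariance rk with Week 4. Then

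Var(ANCOVA) / Var(change) = [1 − (rk)²/vb] / [1 + vb − 2rk].

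Example, r = 0.5 and k = 1: vb = 0.75, and the ratio is (1 − 0.25/0.75)/(1 + 0.75 − 1) = 0.667/0.75 = 0.889. So λ = 10/0.889 = 11.25 and, with df 2 and 55, power is 84.0%.

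Power at 20 per arm, with a gender term that explains nothing also in the model (unadjusted 79.3%):

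| k | r = 0.3 | r = 0.5 | r = 0.7 | r = 0.8 |
|---|---|---|---|---|
| 1 | 87.0% | 84.0% | 81.8% | 80.8% |
| 0.9 | 84.7% | 81.7% | 79.7% | 79.3% |
| 0.8 | 82.7% | 80.1% | 79.3% | 80.3% |

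The gain is 1.5 to 7.7 points at k = 1 and 0 to 3.4 at k = 0.8. The entry rule ("participants who record a pain scale of 4 or higher on any of the VAS scores", or a GUPI quality-of-life alternative) may narrow the baseline spread and push k below 1. If k were 1.2, power would be 88.7 to 91.6%.

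**3. Gender in the VAS change analysis.** A stable gender difference in pain level cancels in a before/after comparison. In 100,000 simulated null trials (20 per arm, 10 men and 10 women, r = 0.5, a gender shift of 1 SD at both times), the unadjusted change test rejected 5.1% of the time. A test of Week 4 alone rejected 2.4%. Gender therefore matters only through the share of the variance of *change* that it explains:

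| Share | True alpha, unadjusted | Power, unadjusted | Power, adjusted |
|---|---|---|---|
| 0% | 4.9% | 79.5% | 79.4% |
| 5% | 4.2% | 79.5% | 81.4% |
| 10% | 3.7% | 79.8% | 83.6% |
| 20% | 2.3% | 80.2% | 87.8% |

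**4. GUPI.** Simulated trials used integer scores 0–45, baseline mean 25 or 30, SD 6 or 8, and r from 0.3 to 0.8. Adding both baseline and gender to the percentage-change model moved power by −0.8 to +4.5 points if the treatment effect is additive, and by −0.4 to −1.4 if it is proportional. ANCOVA of the Week 4 score, against unadjusted percentage change, moved it by +0.4 to +18 points if additive and −4.7 to +1.0 if proportional.

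**5. Responders.** With illustrative arm rates of 20/40/60% and 10 men and 10 women per arm, a gender gap of 0/10/20/30/40 points gave power 65.5/65.3/65.3/64.9/64.5% for chi-square and 64.9/65.3/66.8/69.7/74.7% for a gender-stratified Cochran-Mantel-Haenszel test. There is no gain up to a 10-point gap.

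**The case against.** The strongest reply is that an unadjusted before/after ANOVA is a legitimate choice that already uses baseline, and that every gain above rests on assumed inputs. That stands, and it limits the point to efficiency. Four further objections also stand:

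- The plan speaks only of gender's potential to confound. It does not claim that gender predicts change, and without that the gender term adds no power to the VAS change analysis.
- A baseline covariate in the GUPI percentage-change model can lose power, so it is not a clear improvement there.
- A gender main effect in the weekly models removes only between-person variance and leaves the treatment-by-time test as it was.
- The 79.3% starting point uses the least favourable layout. With two arms equal and the third 1 SD away, power at 20 per arm is 90.0%.

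A reader might infer a gain of about 14 points for VAS. That needs a single baseline week with r = 0.3 and k = 1 (93.7% against 79.3%), whereas the plan describes a two-week lead-in, for which the largest gain at k = 1 is 7.7. A reader might also take the separate female and male GUPI forms as evidence of a gender effect; separate forms alone do not show one.

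None of this removes the core point: for VAS, adjustment uses data in hand and costs about 0.1 point at worst.

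**Conclusion.** The point holds as a possible loss of precision, mainly in the VAS analysis on which the trial was sized. With the two-week mean baseline, the gain forgone is about 0 to 8 points of power for k from 0.7 to 1, on top of 79.3% at 20 per arm. Any further gain from gender depends on its predicting change.

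Three stronger readings are not supported. The planned tests are not biased or anti-conservative: omitting a balanced prognostic factor lowers the true alpha. The sample-size figure is not wrong at 21 per arm; the gap between 21 and 20 is a separate dropout matter. Nor is baseline ignored, since it enters as the reference for relative change and as the earlier VAS measurement.

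**What to change.** Pre-specify the following before outcomes are examined:

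- **VAS:** replace the before/after ANOVA with an ANCOVA of the Week 4 score on treatment, baseline (mean of weeks 1 and 2) and gender, with Tukey-adjusted contrasts. Absolute change as the response gives the same treatment test. Reconcile this with the percentage-change definition under Outcome Variables, which already differs from the VAS test in Statistical Methods.
- **GUPI:** keep percentage change and add gender as the stratification factor. A baseline-adjusted Week 4 GUPI can be a supporting analysis.
- **Weekly models:** include gender and gender-by-time.
- **Responders:** keep the planned test; a gender-stratified test can be supportive.

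The cost is SAP wording and, for VAS, two error degrees of freedom (79.3% to 79.2% if neither covariate helps). It needs no new data, visits or participants.
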